10.5.1.2 Laboratory abnormalities

For laboratory tests covered by the Common Terminology Criteria for Adverse Events (CTCAE) version 4.03, laboratory data will be graded accordingly. All laboratory values will be converted into SI units. For laboratory tests where grades are not defined by CTCAE, results will be graded by the low/normal/high classifications based on laboratory normal ranges.

The following by-treatment summaries will be generated separately for hematology, biochemistry and urinary laboratory tests by study phase:

- Shift tables using CTCAE grades to compare baseline to the worst on-treatment value.
- For laboratory tests where CTCAE grades are not defined, shift tables using the low/normal/high/(low and high).
- Listing of all laboratory data with values flagged to show the corresponding CTCAE grades and the classifications relative to the laboratory normal ranges.

In addition to the above mentioned tables and listings, other exploratory analyses may be performed as appropriate.

10.5.1.3 Other safety data

Summary statistics for data from other tests will be provided, notable values will be flagged, and any other information collected will be listed as appropriate by study phase. Descriptive summary statistics will be provided for electrocardiogram (ECG) and vital sign data, as follows:

- ECG: Changes from baseline to end of study, and new or worsening abnormalities.
- Vital signs: Summary statistics of raw data and change from baseline values (means, medians, standard deviations) plus newly occurring or worsening abnormalities.

Listings with flagged notable values and any other information collected will be provided as appropriate.

10.5.2 Pharmacokinetics

Plasma concentrations of LDE225 and INC424 will be summarized at each scheduled time point by dose level. Descriptive graphical plots of individual plasma concentrations over time will be generated, along with mean concentration time profiles and trough for LDE225 and INC424. A list of individual concentrations will be provided using FAS.

For Phase Ib and Phase II Stage 1 only, PK parameters listed in [Table 10-3](#) and [Table 10-4](#) will be determined for all PK-evaluable patients using non-compartmental method(s) using WinNonlin or Phoenix WinNonlin (Pharsight, Mountain View, CA). PK parameters will be estimated for Week 1 and Week 9 and reported, when feasible. PK parameters in [Table 10-3](#) and [Table 10-4](#) for LDE225 and INC424 will be descriptively summarized for Week 1 and Week 9 by dose level. For Phase II Stage 2, Ctrough will be descriptively summarized at each scheduled time point and by means of graphical display.

Descriptive statistics (n, mean, SD, CV%, median [range], and geometric mean and CV%) will be presented for all parameters with the exception of Tmax for which median values and ranges will be presented. When a geometric mean is presented, it will be stated as such.

[figure not shown]

Table 10-3 Noncompartmental pharmacokinetic parameters for LDE225 (Phase Ib and Phase II Stage 1 only)

| Term | Definition |
|----------------------|--|
| C _{max} | Maximum observed plasma concentration after drug administration [mass x volume ⁻¹] |
| T _{max} | Time to reach C _{max} [time] |
| AUC _{0-24h} | Area under the concentration-time curve from time zero to 24 hours [mass x time x volume ⁻¹] |

Table 10-4 Noncompartmental pharmacokinetic parameters for INC424 (Phase Ib and Phase II Stage 1 only)

| Term | Definition |
|----------------------|---|
| C _{max} | Maximum observed plasma concentration after drug administration [mass x volume ⁻¹] |
| T _{max} | Time to reach C _{max} [time] |
| AUC _{last} | Area under the concentration-time curve from time zero to the time of last measurable concentration [mass x time x volume ⁻¹] |
| AUC _{0-12h} | Area under the concentration-time curve from time zero to 12 hours extrapolate from AUC _{last} [mass x time x volume ⁻¹] |
| AUC _{inf} | Area under the concentration-time curve from time zero to infinity with extrapolation of the terminal phase [mass x time x volume ⁻¹] |
| T _{1/2} | Elimination half-life associated with the terminal slope (lambda _z) of a semi logarithmic concentration-time curve [time] |
| CL/F | Apparent total plasma clearance of drug after oral administration [volume x time ⁻¹] |
| Racc | Accumulation ratio calculated as AUC on Week 9 Day 1 divided by AUC on Week 1 Day 1 [fold] |
| V _{ss} /F | Apparent volume of distribution at steady state after oral administration [volume] |

10.5.2.1 Data handling principles

All concentrations below the limit of quantitation or missing data will be reported as such in the concentration data listings. Concentrations below the limit of quantitation will be treated as zero in summary statistics.

10.5.3 Biomarkers

This study is not adequately powered to assess specific biomarker-related hypotheses, thus statistical analyses of these data should be considered exploratory in nature. Analytical results from such analyses may be used to generate additional hypotheses that must then be verified with data derived from subsequent clinical trials.

Summary tables, listings and visual displays will be created in order to describe the data, detect trends and draw preliminary conclusions. If sample size permits, advanced analyses may be carried out to better understand the data, refine interpretation and generate more robust hypotheses. Furthermore, additional post hoc exploratory assessments are expected and may be performed. The data analysis will be described in the biomarker analysis plan (BAP).

There may be circumstances when a decision is made to stop sample collection, or not perform or discontinue the analysis of biomarker samples due to either practical or strategic reasons (e.g. issues related to the quality and or quantity of samples, or issues related to the assay that preclude the analysis of samples). Under such circumstances, the number of samples may be inadequate to perform a rigorous data analysis and the available data will only be listed.

10.5.3.1 Outline of the data analysis

The proposed data analysis is aligned with the exploratory biomarker objective of the study protocol. The analysis of biomarker data collected at baseline will include basic descriptive statistics for all enrolled patients and by dosing schedule and/or treatment group and for the full population. If post baseline biomarker data are collected, distribution of change from baseline data will also be described. Where appropriate; baseline values and/or change from baseline values of biomarker and mutational status will be described with respect to clinical endpoints of interest. Exploratory subgroup analysis according to some of the baseline biomarker data may be performed. In addition, the association between biomarker levels or change in biomarker levels with PK, efficacy or safety endpoints may also be explored via suitable statistical analysis or graphical aids. For instance scatter plots/strip plots of biomarkers at baseline versus response may be created. Results from these exploratory analyses may be summarized in the clinical study report or in a separate document.

10.5.3.2 Data handling principles for biomarkers

Detailed data handling methods will be addressed in the RAP or in a stand-alone analysis plan document, as appropriate. These details may include (but are not limited to) descriptions of data transformations, approach to handle measures below the lower limit of quantification (LLOQ), thresholds and algorithms used to categorize and combine biomarkers etc.

10.5.3.3 Data analysis principles

10.5.3.3.1 Analysis sets

The standard analysis sets will be used instead according to the purpose of a given analysis (e.g. FAS to describe biomarkers, safety/per-protocol set to assess the relationship between biomarkers and selected safety/efficacy endpoints). Note that since no imputation is usually planned, the number of patients included in a given analysis will reflect the number of patients in the chosen analysis set which have a valid biomarker assessment.

10.5.3.3.2 Basic tables, figures and listings

Mutations involved in the molecular disease characterization of MF will be listed by patient and summarized using frequency tables by dose cohort. Association with efficacy endpoints (spleen volume reduction) and mutation status will be assessed graphically via strip plots or frequency tables of mutational status group and response categories ($\geq 35\%$ reduction and $< 35\%$ reduction in spleen volume) by dose cohorts.

The expression levels of Hh pathway related biomarkers (such as Gli1), cytokine levels and allele burden (reported as percent mutated) will be reported and summarized as follows:

All data will be listed by dosing schedule, patient and time point. Summary tables of the expression levels will be created at each measured time point by dosing schedule and all dosing groups combined. Summary tables will include number of samples (n), % of those samples below LLOQ, mean, standard deviation, median, %CV, minimum and maximum. For all post-baseline time-points; fold change in biomarker expression levels will also be summarized. The summary statistics will include, number of samples, mean, geometric mean, %CV of geometric mean, minimum, maximum etc. Additionally frequency tables (number and percentage of subjects) for JAK2 mutation status (positive/negative) at baseline will be reported.

Longitudinal plots of the mean fold-change from baseline along with 95% CI's or standard error bars will be created to explore the trend over time. Additionally, a mixed model analysis of \log_2 (fold change from baseline) $\sim \log_2$ (baseline level) + dose schedule + time + dose schedule*time may be carried out. In that case, longitudinal plots of model adjusted means for each dose schedule over time, together with the 95% confidence intervals will be created to view trends over time. Strip plots or scatter plots of baseline or change from baseline in biomarker levels versus end-point of interest (spleen volume reduction) may also be produced to explore the association with efficacy.

The associations between biomarkers and efficacy outcomes may also be explored via more sophisticated statistical models if sufficient data are available.

10.5.3.3.3 Advanced analysis methods

Advanced statistical analysis may be carried out to explore the data in a post-hoc fashion.

These methods will typically be used to build a model to estimate, classify or predict the relationship between the explanatory variable(s) and the dependent variables (e.g. linear mixed models fitted on longitudinal data to quantify time-related changes or models to predict

response based on baseline gene expression levels) or to identify patterns and similarities in the data by establishing relationship among all variables (e.g. hierarchical clustering of patients into subgroups according to their biomarker profile). Variable selection, predictive modeling and surrogacy methodologies may be applied to explain and predict response to treatment.

Details of such methodology if applied to the data will be described in a separate Biomarker Analysis Plan document.

10.5.4 Patient Reported Outcomes (Seven-day modified MFSAF v2.0 and EORTC QLQ-C30)

The Seven-day Total Symptom Score (TSS) and individual item scores from MFSAF will be summarized descriptively along with changes from baseline to each visit where the variable is measured. At week 24 the proportion of patients who have a $\geq 50\%$ reduction from baseline in total symptom score based on the Seven-day modified MFSAF v2.0 will be determined as follows.

[figure not shown]
[figure not shown]
The Seven-day TSS will be defined as the sum of 6 individual symptom scores (each scored on a 0-10 point scale) collected on the same day. The score will be missing if there are any missing individual scores and inactivity will not be included.

[figure not shown]
[figure not shown]
The percent change will be calculated by:

- $\% \text{ change} = 100 \times (\text{Week 24 Total Score} - \text{Baseline Total Score}) / \text{Baseline Total Score}$

The percent of patients who have a $\geq 50\%$ reduction in TSS at week 24 will be estimated with a two-sided 95% confidence interval. Similar summary will be presented for each of the individual symptom scores. A waterfall graph will be presented to display the percent change from baseline in Total Symptom Score for each patient at Week 24.

The EORTC QLQ-C30 subscales and individual item scores will be summarized descriptively along with changes from baseline to each visit where the variable is measured.

10.7 Interim analysis

There will be an interim analysis for both safety and efficacy after 18 patients are enrolled in the phase II study. After the first 18 patients are enrolled and observed over a minimum of 24 weeks or until death, documented disease progression, intolerable toxicity, withdrawal of consent, discontinuation at the discretion of the investigator or lost to follow-up, whichever comes first, further enrollment can be stopped for futility if there are less than 8 responders (i.e., spleen volumetric reduction of at least 35% through MRI/CT). This corresponds to a decision threshold of >20% (Bayesian) predictive probability of success to continue enrollment (Table 10-6).

Review of safety data will include, but is not limited to, assessment of the nature and frequency of deaths during treatment, serious adverse events, Grade 3 or 4 adverse events, key laboratory abnormalities, abnormal results from electrocardiogram (ECG) assessments and distribution of safety-related reasons for discontinuation. The trial might be terminated at the interim if treatment is not well tolerated as determined by steering committee (Grade 3-4 AEs >20% may result in termination).

It is possible to terminate the trial at the interim for lack of adequate efficacy, i.e. futility. Assessment of futility will be based on the calculated Bayesian predictive probabilities for the occurrence of the response rate in the FAS.

The efficacy outcome (response rate) is assumed to be binary, namely, response (achieving \geq 35% reduction of spleen volume from baseline by centralized reviewed MRI/CT, Yes vs. No), and the number of responders follow a binomial distribution.

Suppose the prior belief regarding the probability of response (π) is that it has a beta distribution with parameters α_0 and β_0 . If there are x responders out of n patients, then the posterior distribution for π is beta distribution with parameters $\alpha_1 = \alpha_0 + x$ and $\beta_1 = \beta_0 + n - x$. Now let Y represent the number of success from m future observations, then the posterior predictive distribution of Y conditional on the observed data at the interim (x responders out of n patients) is a betabinomial distribution described by

$$p(Y = y|x, n) = \binom{m}{y} \frac{B(\alpha_0 + x + y, \beta_0 + n - x + m - y)}{B(\alpha_0 + x, \beta_0 + n - x)}$$

Where $B(a,b)$ is the beta distribution with parameter a and b .

The prior for the response rate is assumed to follow a Beta(1,1) distribution, which corresponds to a priori expectation of 50%. If there are 8 or more responders, after the first 18 patients have been observed for 24 weeks, then 28 additional patients will be enrolled into stage 2. Encouraging efficacy will be concluded if the observed ORR exceeds 50% (i.e. 23/46) at the end of Phase II.

In this study, futility is equivalent to observe less than 8 responders in 18 patients (Table 10-6). However, the cut-off for the number of responders needed will be determined at the time of interim analysis based on the actual number of patients enrolled in the study following the algorithm defined in the protocol.

Table 10-6 Predictive probability of observing response rate of 50% (n=18) or greater in the FAS at the primary analysis (46 patients) under different interim results

| Observed response at IA | | Predictive probability of observing response rate $\geq 50\%$ |
|-------------------------|------|---|
| # of response | % | |
| 4 | 22.2 | 0.002 |
| 5 | 27.8 | 0.011 |
| 6 | 33.3 | 0.047 |
| 7 | 38.9 | 0.143 |
| 8 | 44.4 | 0.318 |
| 9 | 50.0 | 0.548 |
| 10 | 55.6 | 0.762 |
| 11 | 61.1 | 0.905 |
| 12 | 66.7 | 0.972 |
| 13 | 72.2 | 0.994 |

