The efficacy of the co-administration of LDE225 and INC424, as determined by splenic volume reduction from baseline, will be evaluated using a Bayesian predictive probability of success (PPOS) index during the phase II portion of the study. Phase II will have a two-stage design. In phase II, encouraging efficacy will be concluded if the proportion of patients achieving a $\geq 35\%$ reduction in spleen volume from baseline, as measured by MRI/CT at 24 weeks, is $\geq 50\%$. At the initial stage (stage 1), 18 patients will be enrolled. An interim analysis will be conducted after the 18 patients in Stage 1 have been observed for 24 weeks or

until death, documented disease progression, initiation of a new MF therapy, intolerable toxicity, withdrawal of consent, discontinuation at the discretion of the investigator or lost to follow-up. If the PPOS exceeds 20% based on Stage 1 patients, equivalent to observing at least 8 responders (i.e., spleen volumetric reduction of at least 35% through MRI/CT) observed over a 24 week period, an additional 28 patients will be enrolled into Stage 2. Encouraging efficacy will be concluded if the observed Overall Response Rate (ORR) exceeds 50% (i.e. 23/46). Additionally, in this Phase II part, the effect of the combination of bone marrow fibrosis and disease-specific pharmacodynamics biomarkers as a function of the molecular disease characterization of myelofibrosis will be evaluated to support the development of patient pre-selection markers.

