Each dose escalation cohort will consist of patients with low ($\leq 200 \times 10^9/L$), high ($> 200 \times 10^9/L$) or both low and high baseline platelet counts. Decisions for the next dose will be made together for all patients, unless thrombocytopenia related dose limiting toxicities (DLTs) are observed, leading to different recommended dose combinations for patients with low and high baseline platelet counts. In this case, Novartis and study investigators may also decide to continue to treat both groups of patients together at the lower of the recommended dose combinations.

If a single MTD and/or RPIID is established for both low and high platelet sub-groups then an additional safety expansion cohort of 6 patients will be enrolled at that dose level to further define the safety and tolerability of the combination. If a single MTD/RPIID is established then all patients in Phase II will receive that dose irrespective of baseline platelet levels.

If separate MTDs and/or RPIIDs are declared for low and high platelet sub-groups due to differential experience relating to thrombocytopenia-related DLTs then a safety expansion cohort of 6 patients per sub-group will be enrolled and treated at the respective MTDs/RPIIDs. However, if deemed appropriate Novartis and the investigators may decide to use the lower MTD/RPIID for all patients in the Phase II portion, regardless of the baseline platelet count. Refer to [Section 6.2.3.1](#) for the definition of the MTD and/or RPIID.

Approximately 36 patients are expected to participate in the dose escalation and safety expansion part. The total number of patients enrolled in the entire study will depend on the number of dose escalation steps and drop-outs.

Once the MTD and/or RPIID is established, efficacy of the oral co-administration therapy through MRI/CT scans measuring splenic volume reduction from baseline will be evaluated using a Bayesian predictive probability of success (PPOS) index during the Phase II portion of the study. In Phase II, encouraging efficacy will be concluded if the proportion of patients achieving a $\geq 35\%$ reduction in spleen volume from baseline, as measured by MRI/CT at 24 weeks, is $\geq 50\%$. Additionally, in this Phase II part, the effect of the combination on bone marrow fibrosis and disease-specific pharmacodynamics biomarkers as a function of the molecular disease characterization of myelofibrosis will be evaluated.

[REDACTED]

[REDACTED]

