10.8 Sample size calculation

The total sample-size for the study will be approximately 82.

Phase Ib: Approximately 36 patients are expected to be enrolled into dose escalation cohorts. Cohorts of 3 to 6 evaluable patients per dose level will typically be enrolled in the dose escalation part including at least 6 evaluable patients at the MTD level. Assuming a total of 5 cohorts, the number of patients during dose escalation is expected to be approximately 30. An additional 6 patients will be treated at the MTD/RPIID during the safety expansion. If two MTDs/RPIIDs are established, each MTD/RPIID will enroll additional 6 patients in the safety expansion.

Phase II: Following the determination of an MTD or RPIID in phase Ib, 18 patients will be enrolled in the first stage and if the criterion is met to continue to stage 2, an additional 28 patients will be enrolled.

Operating Characteristics

Phase Ib: The operating characteristics of the BLRM guided by EWOC used in the study is provided in [Appendix 7 \(Section 14.7\)](#).

Phase II: In terms of the frequentist operating characteristics, based on the sample size of 46 patients in phase II, the design has a false-positive rate (type I error) of 9.5% when the true ORR is 40% (representing no benefit) and a true-positive rate (power) of 90% when the true ORR is 60%. The operating characteristics in this study are in [Table 10-7](#).

Table 10-7 Decision of operating characteristics for the primary endpoint of CLDE225X2216 study design

| True ORR | Probability of observing an ORR $\geq 50\%$ |
|----------|---|
| 0.30 | 0.003 |
| 0.35 | 0.022 |
| 0.40 | 0.095 |
| 0.45 | 0.263 |

| True ORR | Probability of observing an ORR \geq 50% |
|----------|--|
| 0.50 | 0.508 |
| 0.55 | 0.745 |
| 0.60 | 0.900 |
| 0.65 | 0.970 |
| 0.70 | 0.993 |
| 0.75 | 0.999 |

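### The Phase II success rule asks for a response rate above 50% but gives the threshold as 23/46, which is exactly 50%; the printed error rates fit only an at-least-50% rule

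*Protocol*

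**What the plan says.** The strict form of the rule appears twice in the protocol. Section 10.7 reads "Encouraging efficacy will be concluded if the observed ORR exceeds 50% (i.e. 23/46) at the end of Phase II". Section 2.2 ends its account of the two-stage design with "Encouraging efficacy will be concluded if the observed Overall Response Rate (ORR) exceeds 50% (i.e. 23/46".

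The non-strict form appears everywhere else:

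- An earlier sentence of Section 2.2 sets the bar at 50% or more of patients reaching a 35% spleen volume reduction at 24 weeks.
- Section 4.1.1 does the same, in the sentence opening "In Phase II, encouraging efficacy will be concluded if the proportion of patients".
- Table 10-6 is titled "Predictive probability of observing response rate of 50% (n=18) or greater in the FAS at the primary analysis (46 patients" and so on, which counts exactly 50% as a success.
- Table 10-7 in Section 10.8 heads its results column "Probability of observing an ORR" of at least 50%.
- The predictive-probability tables in SAP Sections 3.5.2.1.1 to 3.5.2.1.3 also use at least 50%.

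Section 10.8 gives the design's error rates "based on the sample size of 46 patients in phase II": 9.5% type I error at a true ORR of 40% and 90% power at 60%.

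**The concern.** 23/46 equals 0.500, so it cannot be an example of a rate above 50%. The sentence contradicts its own parenthesis, and the word *exceeds* contradicts the rest of the protocol.

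This is the only numerical success criterion for Phase II, in a single-arm, open-label study. At exactly 23 responders out of 46, the strict wording gives a failure; the bracketed count and the other statements give a success. That choice should not be left until the data have been seen. A reader who applies the strict wording would also be running a design whose error rates are not those in Section 10.8.

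**Working it through.** **Inputs (Protocol Sections 10.7 and 10.8).** Stage 1 n₁ = 18; continue if 8 or more respond; Stage 2 n₂ = 28; total 46; null rate 40%, alternative 60%; Beta(1,1) prior; continue if the predictive probability of success is above 20%.

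**Step 1. The threshold count.** 23/46 = 50.0%. The smallest count strictly above half of 46 is 24 (24/46 = 52.2%). The two readings are therefore t = 23 and t = 24.

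**Step 2. Operating characteristics.** For a true rate p, the exact probability of success is

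P(success) = Σ over x = 8,…,18 of C(18,x) pˣ (1−p)¹⁸⁻ˣ × P(Bin(28,p) ≥ t − x).

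| True ORR | Table 10-7 | t = 23 (at least 50%) | t = 24 (above 50%) |
|---|---|---|---|
| 0.30 | 0.003 | 0.0030 | 0.0012 |
| 0.35 | 0.022 | 0.0222 | 0.0112 |
| 0.40 | 0.095 | 0.0952 | 0.0578 |
| 0.45 | 0.263 | 0.2627 | 0.1868 |
| 0.50 | 0.508 | 0.5080 | 0.4124 |
| 0.55 | 0.745 | 0.7454 | 0.6695 |
| 0.60 | 0.900 | 0.9004 | 0.8630 |
| 0.65 | 0.970 | 0.9702 | 0.9593 |
| 0.70 | 0.993 | 0.9930 | 0.9912 |
| 0.75 | 0.999 | 0.9987 | 0.9986 |

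With t = 23 all ten printed rows are reproduced to three decimals. With t = 24, type I error falls by 0.0952 − 0.0578 = 0.0374 and power by 0.9004 − 0.8630 = 0.0374.

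Ignoring the interim stop does not explain the printed figures: a single-stage test of 46 gives 0.1093 and 0.9364 for 23 or more, and 0.0636 and 0.8907 for 24 or more.

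**Step 3. Chance of landing on the disputed result.** The difference between the two columns is the probability of passing the interim and finishing on exactly 23/46. At a true rate of 50% this is 0.5080 − 0.4124 = 0.0956.

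**Step 4. Interim cut-off.** Given x responders of 18, the number of responders Y among the next 28 is beta-binomial with parameters 1 + x and 1 + 18 − x, and the predictive probability is P(Y ≥ t − x).

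| Responders of 18 | Table 10-6 | t = 23 | t = 24 |
|---|---|---|---|
| 7 | 0.143 | 0.143 | 0.095 |
| 8 | 0.318 | 0.318 | 0.238 |

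All ten rows of Table 10-6 are reproduced with t = 23. Under either reading 8/18 clears 20% and 7/18 does not, so the cut-off does not move.

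**Step 5. Actual Stage 1 size.** SAP Section 3.5.2.1.2 reports 20 patients in Stage 1, 26 to follow, and a cut-off of 9. The same formula then gives 0.0953 and 0.9028 for t = 23, and 0.0580 and 0.8656 for t = 24. The gap is essentially unchanged. The SAP's 53-patient table is unaffected: 53 is odd, so at least 50% and above 50% both mean 27 or more.

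**The case against.** The strongest reply is that the intended rule is easy to recover. Both strict sentences print 23/46, 24/46 appears nowhere, and every other statement and table uses at least 50%. The printed error rates are correctly calculated for that rule. The strict reading lowers type I error, so it adds no false-positive risk.

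The practical effect was also nil. The SAP (Section 1.1 and the update closing Section 3.5.2.1) records that Stage 2 did not open, and the planned primary estimate, a UMVUE with an exact interval, does not depend on the success threshold.

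All of this stands. It makes at least 50% the likely intent and limits the consequence. It does not remove the contradiction: a decision rule should not need to be inferred by outvoting one of its own words, and the SAP never restates the final success rule. When the protocol was last amended, Stage 1 was still under observation and Stage 2 remained possible.

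**Conclusion.** The concern holds. The success threshold is stated in two incompatible ways, and the stated 9.5% and 90% belong only to the at-least-50% version. Under the strict wording the design has 5.8% type I error and 86.3% power, 3.7 percentage points lower on each. These figures assume 18 + 28 patients, continuation at 8/18 or more, and true rates of 40% and 60%.

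This is an inconsistency of wording, not an error in the tables. It matters only at exactly 23 responders of 46, leaves the interim decision unchanged, and was not put to the test because Stage 2 was not opened.

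**What to change.** In Protocol Sections 2.2 and 10.7, replace the strict wording with: the observed ORR is at least 50% (23/46 or more). This agrees with Section 4.1.1 and with Tables 10-6 and 10-7, and no number changes. The SAP could state the same rule once, since it currently gives it only through table headings.

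If strict excess was intended, more has to change. The threshold becomes 24/46, the figures in Section 10.8 become 5.8% and 86.3%, and Tables 10-6 and 10-7 and the SAP's 46-patient tables (Table 3-2 and the first Table 3-3) need recalculating.

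The first option changes a few words in two places. Its only cost is procedural: Protocol Section 12.1 requires a written, approved amendment for any change, so it would sensibly go in with other changes.
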